Overall Aim: Determine the effects of post-CBP fibrinogen transfusion on the neonatal fibrin network to develop effective and safe strategies for managing coagulopathies in neonates. This proposal compares the *in vivo* effect of post-CPB administration of FC, a blood product alternative, to cryoprecipitate on neonatal clot properties. Our previous studies using cryoprecipitate suggest that adult fibrinogen does not seamlessly integrate with neonatal fibrinogen and may result in prolonged clot degradation, thus increasing the risk of thrombotic events. It is unclear if this is a direct result of the adult fibrinogen molecule or the other clot stabilizing factors in cryoprecipitate. This is the first *in vivo* study to 1) compare transfusion of cryoprecipitate to FC on neonatal clot structure, 2) assess the degradation rates between the two types of fibrinogen replacement, and 3) correlate clot structure and kinetics with clinical outcomes.

Central Hypothesis: We hypothesize that FC clots will have similar structural characteristics to clots formed from transfused cryoprecipitate, but that FC clots will be degraded faster by the neonatal fibrinolytic system.

Specific Aims:

Aim 1A: Characterize coagulation factors and properties of clot structure, strength, and polymerization kinetics in neonates undergoing CPB surgery after the transfusion of either FC or cryoprecipitate.

Hypothesis 1A: Clots formed after administration of FC will have similar strength and polymerization kinetics as clots formed with cryoprecipitate.

Aim 1B: Compare clot degradation rates in neonates undergoing CPB surgery prior to transfusion of adult fibrinogen, immediately after the administration of FC or cryoprecipitate, upon arrival to the ICU, and at 24hours post-operatively.

Hypothesis 1B: Clots formed after the administration of FC will have faster degradation times at 24hours than those formed with cryoprecipitate.

Aim 2: To complement aims 1A and 1B, we will examine the correlation of clot structure and kinetics to clinical outcomes with specific attention to: 1) transfusion requirements within 24 hours of surgery; 2) 24-hour chest tube output; 3) evidence of adverse thrombotic events.

Hypothesis 2: Patients who have faster clot degradation times will have decreased risk of post-operative thrombotic events, but no difference in transfusion requirements or chest tube output.

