Aim 2 (Correlation of clot properties to clinical outcomes): Clinical outcome variables will be collected for each patient and correlated to clot properties with specific attention to: 1) transfusions within the first 24 hours of surgery, 2) 24-hour chest tube output, 3) clinical signs and symptoms of postoperative thrombosis. Our multi-site prospective, randomized control trial demonstrated that FC can reduce allogenic blood transfusion in neonates and infants undergoing elective cardiac surgery with CPB when compared to cryoprecipitate. Our proposed laboratory studies use platelet poor plasma to enable us to focus on the contribution of supplemental fibrinogen to neonatal clot kinetics. However, since platelets, particularly the increased dependence on vWF in neonates, also play an important role in post-bypass hemostasis, we plan to correlate clinical characteristics and outcomes with our findings regarding clot kinetics. Clinical outcome variables will be collected for each patient and correlated to clot properties with specific attention to 1) transfusion requirements intraoperatively; 2) transfusion requirements within the first 24 hours of surgery; 3) post-operative bleeding recorded by 24 hour chest tube output; 4) clinical signs and symptoms indicative of postoperative thrombosis; 5) mechanical ventilation time; 6) length of ICU and hospital stay 7) adverse events within seven days of surgery. While our study is not powered to for this outcome, we hope that these data will provide some insight in to the clinical differences between different sources of adult fibrinogen.

Samples Size/Statistical Analysis

Data collected will include demographic data, CBP data, transfusion data, laboratory data and clinical outcomes listed above. As we demonstrated in prior work, neonatal clots prior to transfusion displayed a significantly higher degree of alignment when compared to those composed of adult only or mixed neonatal and adult fibrinogen. Based on our previous data, to detect a difference in degradation times between clots formed with neonatal fibrinogen and clots formed with adult fibrinogen with 80% power, we will enroll a total of 36 patients, with 18 in patients in each arm. All quantitative data will be analyzed using a paired t-test or Wilcoxon rank-sum test to

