determine differences between the two groups. Correlation will be determined by either Pearson correlation or Spearman rank correlation. Significance will be defined by a p-value less than or equal to 0.05.

Adverse Events Reporting

Monitoring of Adverse Events (AE) and Serious Adverse Events (SAE) is an important aspect of clinical trials. After enrollment, the research team will collect the adverse events from the medical record. SAEs will be reported to the IRB within the guidelines set by the IRB. Any serious AE will be immediately reviewed by the PI and a senior cardiac anesthesiologist not involved in the study. Quarterly, study subjects will be reviewed on a case-by-case basis by our Quality Improvement Officer and an experienced cardiac anesthesiologist not involved in the study for review of potential adverse events and whether or not the event was related to the study.

Drug reactions including fever, chills, headache, allergic reactions, or thrombosis are potential risks to this study. The most common adverse reactions observed in clinical studies (frequency >1%) with the study drug, fibrinogen concentrate, were fever and headache. The most serious adverse reactions observed are thrombotic episodes (pulmonary embolism, myocardial infarction, deep vein thrombosis) and anaphylactic reactions. These reactions are similar to those of blood transfusions and specifically, cryoprecipitate. The risks are also comparable to cryoprecipitate. Fibrinogen concentrate has been used in Europe and as part of transfusion algorithms around the United States, including our institution with no increased serious adverse events reported. In our preliminary study, we received an IND exemption for the use of fibrinogen concentrate. Thirty patients under one year of age received fibrinogen concentrate instead of cryoprecipitate to treat postoperative bleeding. There was no significant difference in the rate of adverse events, including postoperative thrombosis, between the fibrinogen concentrate versus the cryoprecipitate group. Based on this data and the need to minimize transfusions in the neonatal population undergoing cardiac surgery with CPB, we are seeking an IND exemption for use of this medication in a randomized, control trial.

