## **Sample Size Considerations**

The primary endpoint of the study, on which the statistical power is based, is the difference in clot degradation time at 24 hours post-operatively in neonates randomized to Cyro compared to those randomized to FC, with the primary focus on the overall set of subjects in the ITT population. Based on our previous work comparing adult and neonates, we observed a large difference (>2 standard deviation (SD) difference) in degradation times between the adults and neonates. In this study, we conservatively estimate a 1 SD difference in mean degradation times when comparing degradation times between infants randomized to Cyro vs. those randomized to FC. Assuming a two-sided test at the 5% significance level, 17 completed participants will provide 80% power to detect a 1 SD difference in mean degradation times between our two groups at 24-hours post-operative. Power was calculated using a two-sample t-test. Additionally, assuming an attrition of 1 per group (i.e., death before 24 hour endpoint), 18 participants are// needed for enrollment into the study to ensure an adequate number of subjects complete the primary endpoint. Power calculations were made using PASS v. 14.0.8 (Kaysville, UT).

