## **General Statistical Considerations**

Descriptive statistics will be calculated for all variables of interest. For continuous variables this will include means and standard deviations, medians, quartiles (25th, 75th), minimum and maximum values. Categorical data will be described using counts and percentages. Continuous data will be assessed for normality using histograms and normal probability plots and statistically tested using the Anderson-Darling test and/or the Shapiro Wilk test for normality. Non-normal data will be presented using medians accompanied by 25th and 75th percentiles.

No adjustments will be made for testing multiple secondary and exploratory efficacy outcomes. Given the large number of secondary/exploratory outcomes, the p-values associated with such outcomes will be considered descriptive as the likelihood of making a type I error is inflated due to multiple testing. All analyses will be conducted using SAS v. 9.4 (Cary, NC) or CRAN R v. 3.3 or above (Vienna, Austria). All statistical testing will be two-sided and performed using a 0.05 significance level (i.e., alpha =0.05). Missing values at baseline will be imputed using group median values at the specific time points. We will also repeat all analyses without imputation as a sensitivity analysis.

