### **Analysis of Primary and Secondary Outcomes:**

The primary endpoint of the study is the percentage change of normalized degradation at 24h post-surgery. Primary comparison will be the difference of the primary endpoint between neonates randomized to Cyro and those randomized to FC, with the primary focus on 24h post-surgery time point. To answer this primary research question, we will utilize two sample t-test or Wilcoxon rank sum tests to compare percent change from pre-surgery (baseline) between groups at 24h post-surgery. We will further employ linear mixed models to analyze the longitudinal endpoints accounting for repeated measures. Specifically, we will examine percentage change of normalized degradation at follow up time points (i.e., post-surgery, ICU admission, and 24h post-surgery) relative to baseline between the two groups. Random intercepts at patient level will be included to account for within-subject correlation. Post-hoc comparison between time points will be conducted by contrasts. Results will be presented as difference in least square means between groups or between time points, with associated 95% confidence intervals. Analysis of secondary outcomes, including measurements collected post-transfusion, will be analyzed using similar methods.

Finally, two sample t-tests or Wilcoxon rank sum tests will be used to examine the difference in clot kinetics (i.e., structure, polymerization, degradation) and clinical outcomes including chest tube output, 24-transfusion needs, and ICU length of stay. Two-sample t-tests or Wilcoxon rank sum tests will be used to compare measures between patients with and without thrombotic events. Multivariable linear regression for continuous outcomes and logistic regression for binary outcomes will be used to examine the association between the clot kinetics and clinical outcome while adjusting for potential confounders including pre-surgical weight, age, cardiac diagnosis/ RACHS score, and pre-operative comorbid conditions, as needed.

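### Aim 2's association analyses do not name treatment group, so a pooled link between clot degradation and transfusion could reflect arm alone

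*SAP*

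**What the plan says.** **Planned association analyses.** The protocol (Samples Size/Statistical Analysis) states: "Correlation will be determined by either Pearson correlation or Spearman rank correlation". It mentions no covariates, stratification or partialling by arm. The SAP (Analysis of Primary and Secondary Outcomes) adds linear or logistic regression of clinical outcome on clot kinetics, "adjusting for potential confounders including pre-surgical weight, age, cardiac diagnosis/ RACHS score, and pre-operative comorbid conditions, as needed". Treatment group is named as a model term only in the SAP's Exploratory Subgroup Analysis, through its interaction with subgroup.

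**Expected effects of arm.** Hypothesis 1B (protocol, Specific Aims) reads: "Clots formed after the administration of FC will have faster degradation times at 24hours than those formed with cryoprecipitate". The SAP (Sample Size Considerations) sizes this: "we conservatively estimate a 1 SD difference in mean degradation times". On transfusion, the protocol's Aim 2 text says that the group's earlier multi-site trial "demonstrated that FC can reduce allogenic blood transfusion in neonates and infants undergoing elective cardiac surgery with CPB when compared to cryoprecipitate". It gives no effect size.

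**The prediction under test.** Hypothesis 2 says that patients with faster degradation will have "decreased risk of post-operative thrombotic events, but no difference in transfusion requirements or chest tube output".

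**Status of the aim.** The protocol says that the study is not powered for these clinical outcomes. The SAP (General Statistical Considerations) says that, for secondary and exploratory outcomes, "the p-values associated with such outcomes will be considered descriptive".

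**The concern.** Suppose arm shifts both degradation time and transfusion. The two variables will then be correlated across all infants even if, within each arm, an infant's degradation time says nothing about how much that infant is transfused. Both suggested effects of FC run the same way (shorter degradation time, less transfusion), so the induced association between degradation time and transfusion is positive. Hypothesis 2 predicts none.

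The named covariates would not remove this. They are pre-surgical characteristics, which randomization balances between arms in expectation.

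What is at stake is interpretation. A reader of an unadjusted correlation cannot tell a patient-level link from a difference between the two products, and might take the second as evidence against Hypothesis 2.

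**Working it through.** **1. The plan's own figure.** Inputs from the SAP: two-sided 5%, 80% power, 1 SD difference, two-sample t-test, 17 completers (read as per arm), 18 with attrition. The noncentral t calculation gives n = 16.7, so 17 per arm, with power 80.7% at 17. The figure reproduces. I use 17 per arm and the 1 SD degradation shift below.

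**2. Correlation induced by arm alone.** Let d1 and d2 be the arm differences in degradation and transfusion, in within-arm SDs. With 1:1 allocation and zero within-arm correlation,

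r = (d1·d2/4) / √[(1 + d1²/4)(1 + d2²/4)].

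With d1 = 1 and d2 = 0.5: r = 0.125 / √(1.25 × 1.0625) = 0.108. With d2 = 1: r = 0.25 / 1.25 = 0.20. The documents give no value for d2, so it is an assumption, shown over a range.

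**3. How often the pooled result reaches p<=0.05.** Normal data, 17 per arm, d1 = 1, no within-arm link, 60,000 simulated trials per cell:

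| Assumed transfusion shift (SD) | Mean pooled r | Pooled Pearson, p<=0.05 | Partial correlation given arm, p<=0.05 |
|---|---|---|---|
| 0.25 | 0.06 | 6.1% | 5.0% |
| 0.5 | 0.11 | 9.4% | 4.9% |
| 0.75 | 0.16 | 14.3% | 4.8% |
| 1 | 0.20 | 20.9% | 5.0% |

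Spearman gives almost the same rates: 6.1, 9.5, 14.5 and 21.2%.

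**4. Sensitivity.** If degradation shifts by only 0.5 SD, the pooled rates are 5.4, 6.3, 7.5 and 9.3%. If the transfusion shift were 1.5 SD (with d1 = 1), the rate would be 35%. The documents do not say whether the allocated cryoprecipitate itself counts as a transfusion. If it does, the shift would be larger than otherwise.

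**5. Price of adjusting.** At d1 = 1, arm explains 0.25/1.25 = 0.20 of the variance in degradation. Variance inflation for the clot term is 1/(1 − 0.20) = 1.25, so its standard error is √1.25 = 1.12 times as large, plus one degree of freedom. As an unfavourable case for adjustment, assume a within-arm r of 0.3 and an arm effect on transfusion that runs only through degradation (shift 0.3 SD). Detection is then 49.8% pooled and 40.7% adjusted.

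The simulation models the bare correlation, not the SAP regression with its other covariates.

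**The case against.** **The plan does not exclude arm.** The SAP list is illustrative and to be applied as needed, so treatment group could be added, and neither document says that the arms are pooled. This stands: pooling is inferred from the absence of any within-arm or adjusted analysis. But the protocol's correlations have no covariate list at all, and as-needed wording leaves the choice open until the data are seen.

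**The arm effect on transfusion is weakly supported.** No hypothesis of this trial predicts one. It rests on one background sentence about an earlier trial in neonates and infants, with no size. This also stands, and is why the size is shown over a range.

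**Misreading is already limited.** The aim is unpowered and its p-values are descriptive. The same SAP paragraph plans two-sample tests that include transfusion. If these compare arms (the grouping is not stated), they would alert the reader. This lowers the importance, but a descriptive label does not say whether an association is between patients or between products.

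**Adjustment changes the question.** Hypothesis 2 concerns patients across the whole cohort, and if arm acts only through degradation, adjusting discards useful variation. This is fair, and is the reason to report both results rather than replace one.

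**Timing.** The 1 SD shift is for degradation at 24 hours, while the transfusions counted are intraoperative or within 24 hours and so largely precede that sample. The documents do not say which sample enters the correlation, and the pre-bypass sample precedes randomization, so arm cannot affect it. This stands: arm adjustment does not settle direction.

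**Conclusion.** The point holds as a cheap improvement to a secondary aim. For degradation versus transfusion, the plan as written can produce an association due to arm alone. Under the assumptions shown (17 per arm, 1 SD degradation shift, normal data, no within-arm link), it would do so at p<=0.05 in about 6 to 21% of trials for transfusion shifts of 0.25 to 1 SD, against 5% with arm included. Below about 0.75 SD the excess is modest, and nothing in the documents shows that the shift is that large.

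A reader might infer more than this:
- That the pooled correlation is invalid. It is a legitimate description of all infants; it only cannot separate the two sources of association.
- That the SAP rules out adjusting for arm. Its open list does not.
- That the same problem affects chest tube output or the other clot measures. The documents predict no arm effect on chest tube output, and Hypothesis 1A expects similar strength and polymerization in the two arms.
- That the trial's main result is in doubt. The randomized comparison of degradation at 24 hours and the sample size of 36 do not depend on these analyses.

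**What to change.** Before data lock, add to the SAP that, for degradation versus transfusion, treatment group is a covariate in the association regression, and that the arm-adjusted partial correlation is reported beside the pooled correlation. Hypothesis 2 should be read on both results. The text should also note that transfusions within 24 hours largely precede the 24-hour sample, so neither result establishes direction.

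The cost is wording only: no new data, and the pooled estimate stays. The adjusted estimate loses one degree of freedom and some precision (variance inflation of about 1.25 for the clot term at a 1 SD shift). In the unfavourable case above, that means about 40% detection against 50%.

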### **Exploratory Subgroup Analysis**

Given the sample size of our current study, we are likely underpowered to examine differences in outcomes when stratified by subgroups including race, sex, risk of bleeding and underlying morphology. Nevertheless, we will perform subgroup analyses to examine differences in primary and secondary outcomes within and between subgroups of interest. This will include stratified analyses and by including the interaction between treatment group (FC vs. Cryo) and subgroup in subsequent models.
